This is a randomized, blinded, placebo-controlled pilot study. A stratified block randomization procedure will be used to ensure that each group has an equal number of men, and an equal number of women. Blocks will be made in groups of 4 for each sex. Given that the majority of cardiac surgery patients are male, each group is not expected to be made of an equal number of men and women. The randomization procedure will be done with preprepared numbered envelopes. Separate piles of envelopes will be kept to randomize each sex separately. Each envelope will contain the group assignment of either "Ketamine" or "Placebo". Group assignment papers will be inserted in the envelopes in a random order. A list of the group assignment in each numbered envelope will be kept separate from study materials while the study is being carried out. This measure will help ensure that the research coordinator will be blinded during data collection. A separate list will be made by a coinvestigator not involved in the data analysis denoting which envelopes corresponded to "Group A" and "Group B" to allow for the primary investigator to be blinded during data analysis, and for the study coordinator to ensure stratified randomization has distributed an equal number of patients of each sex in each group by the end of the study.

Either the cardiac surgeon, the cardiac anesthetist or a nurse involved in the patients' care will ask the patient if the research coordinator can approach the patient to discuss

inclusion in the study. The research coordinator will then discuss risks and benefits of being included in the study and obtain consent.

On the day of the procedure the research coordinator will randomly select a numbered envelope for the appropriate sex, and hand this to one of the two other co-investigators prior to surgery. One of the two co-investigators will prepare the study drug.

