Postoperative opioids will be prescribed at a dose and frequency according to the standard postoperative orders for cardiac surgery patients. An intensive care nurse will administer opioids at the doses prescribed on the post-operative orders. This strict protocol for pain management improves the internal validity of the trial, understanding that this may

somewhat decrease external validity in comparison to other centers who do not manage postoperative pain with the same regimen.

Outcomes

The primary outcome is the quantity of opioid administered over the first 48 hours postoperatively. Forty-eight hours was selected as the duration to monitor opioid consumption, as this is the period during which pain post-cardiac surgery has been shown to be most intense. This primary outcome was selected as it will be reliably documented and straightforward to assess, given the strict guidelines for documentation of opioids.

There will be several secondary outcomes. The quantity of opioids used at 24 hours will be noted. Postoperative pain will be measured daily via the "brief pain inventory" by the research coordinator on postoperative days 0, 1, and 2.¹³ Patients will be asked their current pain, the worst and best pain levels throughout the day, as well as their average pain levels. The need for additional analgesic medications will be assessed as a binary outcome for each type of additional medication (NSAIDs, additional opioids, gabapentinoids, etc), measuring whether or not additional agents are added to treat poorly controlled pain. Additional analgesics would likely affect the dose of post-operative opioids administered, making it a co-intervention which may need to be accounted for in the analysis. The presence or absence of postoperative nausea and vomiting requiring treatment, as well as the diagnosis of delirium will be measured as binary outcomes. Intensive care unit and hospital length of stay will be measured in number of days, while the time to extubation, time to first mobilization to a chair, and time to first ambulation will be measured in number of hours after arrival to the intensive care unit through

chart review. While the dose of ketamine used in this study is not likely to cause psychological side effects, the number of patients reporting hallucinations or severe nightmares will be tracked.

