On follow-up phone call at 3 and 6 months patients will be asked whether or not they have persistent pain at the site of the sternotomy. Whether or not persistent pain is present will be noted, along with any medications that they may be taking for the pain. If persistent pain is present, they will be asked ten yes or no descriptive questions about the pain concerning to determine if it is neuropathic in origin.¹⁴ The answer to each question, as well as the overall score will be noted.

Confounders

Possible baseline confounders will be tracked to look for differential distribution between intervention groups. These will include age, sex, body mass index, left internal mammary harvesting. We will stratify our randomization by sex to ensure sexes are balanced in the 2 groups, as sex has been shown to be one of the main confounders for postoperative pain. With a relatively small sample size of 80 patients, a differential distribution of confounders between groups is possible, and an adjustment will be done in our analysis for any factor that is differentially distributed. Injuries during cardiac surgery such as rib fracture and dislocation, or fractured sternum may contribute to postoperative pain as well. Unfortunately, these variables often go undetected and cannot be adequately tracked. We will therefore rely on randomization to ensure equal distribution in both groups.

Analysis Plan

While nearly complete compliance is expected with the therapy, an intention-to-treat analysis will be performed in case any unforeseen issues with compliance arise during the study. Continuous data such as postoperative opioid dose, intensive care unit and hospital length of stay, and time to mobilization and ambulation will be evaluated using the t test if it is determined that the means are normally distributed, or the Wilcoxon Rank Sum test if the means are not normally distributed. Ordinal data such as visual analog scale scores and binary data such as need for additional analgesics and the presence or absence of PONV will be evaluated by a Chi-Square test. If confounding is suspected due to baseline differences in the variables noted above, we will perform a propensity score depending on the variable(s) and the size of the difference. As a secondary analysis, data will be analyzed in subgroups by sex to look for any potential difference in response.

Sample Size & Power Analysis

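### Randomisation is stratified by sex, but the default test of 48-hour opioid dose ignores sex; the cost is precision, and analysing by stratum recovers it at almost no cost

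*Combined protocol and SAP*

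**What the plan says.** Study Design: "A stratified block randomization procedure will be used to ensure that each group has an equal number of men", and likewise of women. "Blocks will be made in groups of 4 for each sex". On the day of surgery, "the research coordinator will randomly select a numbered envelope for the appropriate sex".

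Confounders gives the reason for stratifying: "sex has been shown to be one of the main confounders for postoperative pain". It also lists the baseline factors to be tracked: "These will include age, sex, body mass index, left internal mammary harvesting". Any of these that turns out to be unevenly distributed is to be adjusted for.

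Analysis Plan: continuous outcomes, including postoperative opioid dose, "will be evaluated using the t test if it is determined that the means are normally distributed, or the Wilcoxon Rank Sum test". If baseline differences raise a suspicion of confounding, a propensity score follows, and its use varies with the variable and with how large the difference is. Sex otherwise appears only in a secondary subgroup analysis.

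Sample Size & Power Analysis: a control mean of 125 mg, an SD of 45 mg in both groups, a 25% reduction, two-sided alpha 0.05, and a target of 80 patients.

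**The concern.** Stratifying on a prognostic factor makes the arms more alike on that factor than simple randomisation would. A two-sample test that ignores the factor still counts the between-sex variation as noise, so its standard error is too large. The test becomes conservative, and the benefit built into the design is not collected in the analysis.

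The imbalance trigger does not repair this. If blocks are followed, it will seldom pick up the one factor that was deliberately balanced.

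For the other factors the trigger has a different weakness. Chance imbalance, judged against no stated threshold, decides whether an adjusted result exists, and the plan does not say whether that result or the unadjusted one is primary.

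**Working it through.** **1. The plan's own figures.** The difference sought is 0.25 × 125 = 31.25 mg, with SD 45 mg. The noncentral t distribution gives 34 per arm for 80% power and 45 per arm for 90%, as the protocol states. At 40 per arm, the noncentrality is (31.25/45) × √(40/2) = 3.11 and power is 86.6%. The claim of more than 80% is correct.

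**2. Can the trigger bring sex in?** With blocks of 4 used in order, an incomplete last block leaves a stratum at most 2 patients apart between arms. With 10 women, the worst case is 6/40 v 4/40 (chi-square p = 0.50). With 22 women it is 12/40 v 10/40 (p = 0.62). A significance-based trigger would not fire.

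**3. Cost of leaving sex out.** The documents give neither the share of women nor a sex effect on dose. Assumed: 20 women and 60 men, total SD 45 mg, additive effects, normal doses, block order.
- Share of variance due to sex: R² = g² × 0.25 × 0.75 / 45², where g is the sex difference in mg.
- Ratio of unadjusted to sex-adjusted standard error: 1/√(1 − R²).
- For g = 33: R² = 204.2/2025 = 0.101, ratio 1.055.

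Type I error and power come from 6,000 simulated trials per setting (Monte Carlo error about 0.3 and 0.4 points). Each used t or Wilcoxon according to a Shapiro-Wilk check at 0.05, or the same choice analysed by sex.

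| g (mg) | R² | SE ratio | Type I error, plan | Type I error, by sex | Power at 25%, plan | Power at 25%, by sex | Gain (points) |
|---|---|---|---|---|---|---|---|
| 10 | 0.009 | 1.005 | 5.2% | 5.3% | 86.6% | 86.8% | 0.2 |
| 20 | 0.037 | 1.019 | 4.5% | 4.9% | 87.3% | 88.1% | 0.8 |
| 33 | 0.101 | 1.055 | 3.7% | 4.7% | 87.7% | 89.4% | 1.7 |
| 45 | 0.188 | 1.109 | 3.1% | 5.2% | 89.0% | 93.0% | 4.0 |

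A closed-form check agrees. Two-sided type I error of the unadjusted t test is about 2 × P(t₇₈ > 1.991 × ratio), which gives 4.9, 4.6, 3.9 and 3.0%. Power of the sex model, with SD 45√(1 − R²) and 77 degrees of freedom, is 86.9, 87.8, 89.9 and 92.5%.

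At a 20% effect (25 mg, the size of reduction that Background reports for the earlier cardiac surgery trial), the simulated gains are 0.2, 1.3, 3.7 and 6.2 points.

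**4. If envelopes are drawn at random from a large pile.** Type I error of the plan's test is then about 5%. A sex trigger at p<0.10 would fire in about 11% of trials. The gain from analysing by sex is −0.1, 0.9, 3.4 and 5.5 points. The loss is then one of precision only.

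**5. The trigger for the other factors.** Age, BMI and left internal mammary harvesting are not stratified. Treat them as three independent, approximately normal factors (an assumption). If each is flagged with chance a, at least one is flagged with chance 1 − (1 − a)³.
- p<0.05: 1 − 0.95³ = 14%.
- p<0.10: 1 − 0.90³ = 27%.
- Standardised difference above 0.2: a = P(|Z| > 0.2/√(2/40)) = 0.371, giving 75%.
- Standardised difference above 0.1: a = 0.655, giving 96%.

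For age and BMI alone (jointly explaining an assumed 5% of variance, 25% effect, normal doses, score used as a covariate), the trigger fires and also moves the result across 0.05 in about 1%, 1.5%, 3–4% and 4–5% of trials at these four thresholds.

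**The case against.** The strongest reply is that the missing sex term is a matter of preference: no bias, no inflated type I error, and power already above target. That is right as far as it goes. The larger gains also need sex differences of 33 or 45 mg, both above the 31.25 mg treatment effect sought. The protocol links sex to postoperative pain, not to opioid dose, so no sex effect on the primary outcome can be read from it. The conservatism and the 2-patient limit both depend on block order, which the envelope wording leaves open. All of this stands, and it is why the point is one of precision at a range of assumed values.

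On the trigger, Study Design provides coded groups "to allow for the primary investigator to be blinded during data analysis", which limits selective choice. Even if the most favourable of the planned test and three propensity forms were taken in every null trial, simulated type I error is 6.7, 6.1, 5.5 and 4.2% for the four sex differences. That is at most 1.7 points above nominal. Coded labels still leave baseline differences and candidate p-values visible, so blinding narrows the choice without fixing it.

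A reader might infer more in three places:
- **That the primary result is biased or the trial too small.** The stated sample sizes reproduce, and nothing here changes them.
- **That adjusted and unadjusted results would conflict in 4–5% of trials in general.** That holds only at the loosest threshold; where the trigger must fire at p<0.05 it is about 1%.
- **That the plan will adjust for additional analgesics given after randomisation.** Outcomes says only, of those analgesics, "making it a co-intervention which may need to be accounted for in the analysis", and the Analysis Plan does not take this up.

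**Conclusion.** The concern holds as a precision point. Sex is used in the randomisation and left out of the default primary test. With block order, 60 men and 20 women, normal doses and total SD 45 mg, this costs about 0.2 to 4 points of power at the 25% effect for assumed sex differences of 10 to 45 mg, and type I error drops to about 3% at the top of that range. If sex does not affect opioid dose, nothing is lost.

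The secondary point also holds. Whether an adjusted analysis is produced depends on chance imbalance, with a frequency anywhere from 14% to 96% according to a threshold that the plan does not give. Its effect on the significance of the primary result is small, at about 1% to 5% of trials for age and BMI.

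The change is worth making because it is nearly free. The missing normality criterion and the remark on additional analgesics could usefully be clarified, but they are not part of this finding.

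**What to change.** Before the group labels are broken, amend the Analysis Plan as follows.

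- **Primary analysis.** Analyse 48-hour opioid dose by the randomisation stratum. Where the plan selects the t test, use a linear model with treatment and sex. Where it selects the rank test, use a sex-stratified Wilcoxon (van Elteren) test. Report the sex-adjusted mean difference in mg with its 95% confidence interval.
- **Status.** State that this is the primary result whatever baseline imbalance is seen.
- **Other factors.** For the primary outcome, replace the imbalance-triggered propensity score with one fixed sensitivity model: treatment, sex, age, BMI and left internal mammary harvesting. Drop the last if nearly all patients have it.

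The cost is wording only, since these factors are already to be recorded. The sex term uses one degree of freedom. If sex has no effect, simulated power at the 25% effect changes by +0.1 points with normal doses, −0.5 with moderately skewed doses (90.9% to 90.4%) and −0.1 with strongly skewed doses. The sample size does not change.

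### Ordinal pain scores are assigned a chi-square test, which ignores their order and can lose half or more of the power for modest differences

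*Combined protocol and SAP*

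**What the plan says.** The Analysis Plan section sets tests by type of data.

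- Continuous outcomes get a t test, "or the Wilcoxon Rank Sum test if the means are not normally distributed".
- The next sentence covers ordinal and binary outcomes together. It groups "Ordinal data such as visual analog scale scores and binary data such as need for additional analgesics" with nausea and vomiting, and names a single test for all of them: they "will be evaluated by a Chi-Square test".

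No trend version, banding or cut-point is given for the ordinal scores, and no other section assigns them a different test.

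The Outcomes section lists the pain ratings among the secondary outcomes. They come from the brief pain inventory, administered by the research coordinator on postoperative days 0, 1 and 2: "Patients will be asked their current pain, the worst and best pain levels throughout the day, as well as their average pain levels". It does not mention a visual analog scale. The same section records added analgesics as yes/no outcomes, "measuring whether or not additional agents are added to treat poorly controlled pain".

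**The concern.** Chi-square suits the binary outcomes in that sentence. For pain scores it discards the information that matters, namely that 3 is less pain than 4 and 4 is less than 5. A consistent downward shift in one arm is spread over as many degrees of freedom as there are score levels less one, so a modest real difference is likely to be missed. A significant result would show only that the two distributions differ somewhere.

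The primary outcome counts opioid given over 48 hours. The Strengths & Limitations section acknowledges that patients differ in when they ask for analgesia and nurses in when they give it. The day 0-2 ratings are the patients' own account of pain in that period. With the record of added analgesics, they help show whether lower opioid use came with equal or better pain control. That role is an inference, as the protocol does not spell it out. A non-significant chi-square result could be misread as no difference in pain.

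The two sections also name different instruments, so the analysis text does not name the scores that will be collected.

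**Working it through.** **1. The plan's own figures, to fix the sample size.** From Sample Size & Power Analysis: control mean 125 mg, SD 45 mg, 25% reduction, two-sided alpha 0.05.

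- Difference = 0.25 × 125 = 31.25 mg; standardised effect = 31.25 / 45 = 0.69.
- n per arm = 2(z₀.₉₇₅ + z_power)² / 0.694². At 80% power: 2 × 7.849 / 0.482 = 32.5, so 33. At 90%: 2 × 10.507 / 0.482 = 43.6, so 44.
- Using the t distribution: 33.5, so 34 (68 in total), and 44.6, so 45 (90 in total). Both match the plan.
- Power at the planned 40 per arm is 0.866, consistent with the stated figure of over 80%.

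The primary calculation reproduces, and 40 per arm is used below.

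**2. Why the test ignores order.** With equal arms, and counts a_j and b_j at score level j, Pearson's statistic is X² = Σ_j (a_j − b_j)² / (a_j + b_j), on (levels − 1) degrees of freedom. Reordering the levels leaves the sum unchanged, and squaring removes the sign of every difference.

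**3. Degrees-of-freedom check.** For a shift of d SDs with n per arm, the noncentrality is about λ = n d² / 2. At d = 0.5, λ = 40 × 0.25 / 2 = 5. Power at the same λ, alpha 0.05:

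| d | λ | 1 df (uses order) | 3 df (four bands) | 10 df (11 levels) |
|---|---|---|---|---|
| 0.3 | 1.8 | 27% | 18% | 11% |
| 0.4 | 3.2 | 43% | 29% | 18% |
| 0.5 | 5.0 | 61% | 44% | 27% |
| 0.69 | 9.6 | 87% | 74% | 52% |

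This is a large-sample benchmark. Here 40 patients per arm over 11 levels average 40 / 11 = 3.6 expected per cell, so it flatters the chi-square test.

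**4. Simulation.** Assumptions, none of which the documents give for pain scores: normal scores rounded and clipped to 0-10, SD 2 or 2.5, control mean 4 or 5. There were 10,000 trials per setting, with two-sided tests at 0.05. Pearson chi-square was applied to the observed levels and to four assumed bands (0, 1-3, 4-6, 7-10). The comparator is the tie-corrected Wilcoxon test, with continuity correction, on ungrouped scores. Relative loss = 1 − chi-square power / Wilcoxon power. One point is 1 / 2.5 = 0.4 SD to 1 / 2 = 0.5 SD.

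| Difference | Chi-square, ungrouped | Wilcoxon | Loss | Chi-square, four bands | Loss |
|---|---|---|---|---|---|
| 1 point | 11-21% | 40-57% | 64-71% | 23-34% | 40-42% |
| 1.5 points | 28-50% | 73-89% | 44-62% | 51-70% | 22-30% |
| 2 points | 52-82% | 92-99% | 17-44% | 78-93% | 6-15% |

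With no difference, ungrouped chi-square rejects in 3.2-3.6% of trials and Wilcoxon in 4.6-5.1%. Ungrouped, 52-69% of expected cells are below 5. A repeat with new random numbers moved the ends of the power ranges by no more than about 2 percentage points.

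**5. Sensitivity.**

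- At 0.69 SD, the primary outcome's standardised effect, and with control means 3-5, ungrouped power is about 36-46% against 83-85%.
- With three categories the loss is 22% at 0.3 SD and 20% at 0.5 SD, here against Wilcoxon on the same categories.
- On an ungrouped 0-100 integer scale, chi-square has at most 0.5% power up to 0.69 SD.

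**The case against.** The strongest reply is that losing half or more of the power depends on leaving scores ungrouped. The plan does not say that they will be tabulated level by level. With so many small expected cells an analyst might well collapse them, and then the loss is at most 42% with four bands and about 20% with three categories. Even ungrouped, it falls below half over part of the 1.5-point range and all of the 2-point range. This stands as a limit on size. It does not rescue the stated test: banding reduces the loss without removing it, and bands chosen after seeing the data would be an unplanned decision.

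Second, every input to the pain-score calculation is assumed. That is correct, which is why ranges are shown. The test assignment and its blindness to order do not depend on those inputs.

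Third, the ordinal rule gives the visual analog scale only as an example, so brief pain inventory ratings fall under it. That is the natural reading, and the power comparison relies on it. What remains is a mismatch in the instrument's name.

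Fourth, this is a pilot powered for opioid use alone, with pain scores among many secondary outcomes. That limits the seriousness of the point, though the correction costs almost nothing.

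**Conclusion.** The concern holds. The plan calls the pain scores ordinal and then assigns a test that ignores order, while reserving the rank-sum test for continuous data. With 40 per arm and ungrouped 0-10 scores (SD 2-2.5, control mean 4 or 5), the stated test loses roughly two thirds of the available power at 1 point, about half at 1.5 points, and less at 2 points. With four bands the loss at 1 point is about 40%. These sizes rest on assumed score distributions; the mismatch between test and data does not.

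The stated test is mildly conservative, so it adds no false-positive risk. The primary opioid outcome, its sample size, and the yes/no persistent-pain and additional-analgesic outcomes are unaffected. This should be corrected, but it does not threaten the main comparison.

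**What to change.** In the Analysis Plan section:

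- Replace the reference to visual analog scale scores with the brief pain inventory items listed under Outcomes (current, worst, best and average pain on days 0, 1 and 2).
- State that these items will be compared between arms with the Wilcoxon rank-sum test already in the plan, or with a proportional-odds model.
- Limit the chi-square test to binary outcomes.

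A repeated-measures model, or naming one key pain item, is optional.

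The cost is a wording change. The data collected, the sample size and the primary analysis stay as they are.

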Pilot Study: The Effect of Intraoperative Ketamine on Analgesia Post-Cardiac Surgery and Prevention of Postoperative Pain

JGH Protocol #: 16-289 NCT02925858

Primary Investigator: [name]

Co-Investigator: [name] [name]

Co-Investigator: [name]

Co-Investigator: [name] [name]

Co-Investigator: [name]

Background

Pain control post-sternotomy is an essential part of fast-track surgery, a program to promote early recovery. Up to 75% of patients complain of moderate-to-severe pain after cardiac surgery, with poorly controlled pain leading to an increased risk of myocardial ischemia and chronic post-sternotomy pain, which is seen in 11% of patients. Given the relative contraindications to epidural analgesia and non-steroidal anti-inflammatories after coronary artery bypass grafting (CABG) surgery, options for multimodal analgesia are limited.

Ketamine is an NMDA antagonist which potentiates the release of inhibitory neurotransmitters, modulating the sensory processing of pain.⁴ Ketamine is a well-established treatment for a variety of pain syndromes, and is approved by Health Canada to be used as a supplemental agent during anesthesia.⁵⁻⁷ There is a growing literature showing that Ketamine contributes to pain control after surgery as well. It has been shown that Ketamine decreases opioid needs after spine surgery, as well as after thoractomy.⁸⁻¹⁰ While these studies used the racemic form of Ketamine, the only version approved for use in Canada, a Finnish study on the cardiac surgery population evaluated the S(+) enantiomer of Ketamine, which has not been available in Canada. This was shown to reduce postoperative opioid requirements by 20%.¹¹

There are limited downsides to the administration of Ketamine. The most common adverse effects of ketamine in awake patients include nightmares, hallucinations, a dissociative state, headaches, and hepatotoxicity. ^{5,12} In clinical studies of low dose Ketamine used for perioperative pain control, there has not been shown to be a significant increase in side effects between treatment and placebo groups. ⁹

Ketamine, while used at times, is not routinely used during cardiac anesthetics. It has not been studied for its effect on postoperative pain control and its effect on post-sternotomy chronic pain.

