Given that the S(+) enantiomer of Ketamine previously studied in cardiac surgery patients is not available in Canada, this study will investigate the racemic form of Ketamine that is available in Canada, which, to our knowledge, has not been studied in the cardiac surgery population. This is the form of ketamine will has well established use during anesthesia care and the form of ketamine with which the vast majority of the literature on postoperative pain has been based.

Specific Aim & Hypothesis

The main goal of this pilot study is to assess the effect of an intraoperative intervention, the administration of ketamine, on analgesia post-cardiac surgery. This pilot study will also help assess the feasibility of recruiting and retaining patients, safely administering a blinded medication in the operating room, accurately measuring a primary outcome of postoperative narcotic consumption, and blinding those involved in the care of cardiac surgery patients.

The long-term goal of this study and subsequent follow-up studies is to improve pain control after cardiac surgery, with the hope of allowing patients to perform earlier physiotherapy, regain functional status, and allow for an earlier discharge from hospital.

The specific aim of this study is to ascertain whether an intraoperative infusion of racemic Ketamine can improve postoperative pain control after CABG surgery. The hypothesis is that the intraoperative administration of this medication will improve postoperative pain

control demonstrated through a decrease in postoperative opioid consumption of more than 25%.

Study Design

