Using the data in the trial evaluating S(+)-Ketamine, an estimate of 125mg of oxycodone over the 48 hours post cardiac surgery was used as a baseline.¹ In this same study, both the intervention and controls groups had standard deviation of oxycodone of 45mg. To detect a decrease in opioid requirements of 25% with a power of 80% and a two-sided alpha of 0.05, a total of 68 patients would be required in the trial, with 34 in each group. For a power of 90%, a total of 90 patients would be required in the trial with 45 patients in each arm. The Jewish General Hospital, a McGill University teaching hospital, performs approximately 600 cardiac surgeries per year, with approximately 350 CABG surgeries via sternotomy. The goal will be to

enroll 80 patients. With the nature of this study and the need for hospitalization post-cardiac surgery, there should be minimal, if any, drop-outs or loss to follow-up, and therefore the sample size of 80 patients should allow for a power of over 80%.

Strengths & Limitations

Strengths of the study include the ability to randomize, and the ability to blind the patients, nurses, anesthesiologists and pain evaluators. This study will be performed at a single center, which allows for easier standardization of therapy, at the same time limiting generalizability of the findings. The primary outcome, opioid use, is easily measurable.

Limitations will include the inter-individual variability in both patient thresholds for analgesia request, and nurse thresholds to administer analgesia. Injury during cardiac surgery may contribute to pain (rib fracture or dislocation), and will not be able to be accurately measured.

Timetable

The Jewish General Hospital currently performs approximately 350 CABG surgeries per year, which is approximately 30 per month. Once ethics approval is obtained, and organizational logistics are arranged, the goal would be to recruit 80 patients over the span of four months. Another 2 to 3 months will likely be required for full data analysis and manuscript preparation.

References

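### The plan looks for a difference in ketamine response by sex, but names no analysis that estimates the difference in effect between men and women (minor, cheap to improve)

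*Combined protocol and SAP*

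**What the plan says.** The Analysis Plan gives the sex subgroups one sentence: "As a secondary analysis, data will be analyzed in subgroups by sex to look for any potential difference in response". It names no method for them. For continuous outcomes, the data "will be evaluated using the t test if it is determined that the means are normally distributed, or the Wilcoxon Rank Sum test"; ordinal and binary outcomes go to a chi-square test. A propensity score is held in reserve in case baseline imbalance raises a suspicion of confounding.

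Sex also appears in the design. Under Study Design, "Blocks will be made in groups of 4 for each sex". The Confounders section gives the reason: "sex has been shown to be one of the main confounders for postoperative pain". Study Design expects unequal numbers of men and women ("Given that the majority of cardiac surgery patients are male") but gives no proportion.

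The plan does not say on which scale response is to be compared. Specific Aim & Hypothesis uses a relative scale ("control demonstrated through a decrease in postoperative opioid consumption of more than 25" percent), while the power calculation uses mg of oxycodone.

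**The concern.** Whether response differs by sex depends on one quantity: the ketamine-placebo difference in men minus that difference in women. Each named test, applied within a sex, gives one of those two differences or a p-value for it. Nothing in the plan puts them together or attaches an uncertainty to the contrast. Stratified randomization balances sex between the arms, and the propensity score deals with baseline imbalance. Neither measures effect modification. The Sample Size & Power Analysis section covers only the overall comparison.

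At stake is how the subgroup results will be read. With mostly men, the male subgroup will have much more power than the female one. Two p-values side by side can then look like a sex difference when the effect is the same in both. The primary comparison does not depend on this analysis.

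**Working it through.** **Inputs from the Sample Size & Power Analysis section.** Control mean 125 mg over 48 hours; SD 45 mg ("both the intervention and controls groups had standard deviation of oxycodone of 45mg"); a 25% decrease, so 0.25 × 125 = 31.25 mg; two-sided alpha 0.05; 80 patients, so 40 per arm.

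**Assumptions, not in the documents.** 70%, 80% or 90% men, which gives 12, 8 or 4 women per arm; the same SD in both sexes; normally distributed doses.

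**Step 1: the plan's own figures.** The power of a two-sample t test with n per arm comes from the noncentral t distribution with 2n − 2 df and noncentrality 31.25 / (45 × √(2/n)). The smallest n reaching 80% is 34 per arm (68 in total), and the smallest reaching 90% is 45 per arm (90 in total). Both match the plan. With 40 per arm, power is 86.6%, in line with the stated figure of over 80%.

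**Step 2: the same test within each sex, with a true effect of 31.25 mg in both.** Write p_m and p_w for power in men and women. The subgroups are independent, so the chance that exactly one is significant is p_m(1 − p_w) + p_w(1 − p_m).

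| Women / men per arm | p_w | p_m | Exactly one significant |
|---|---|---|---|
| 4 / 36 | 0.133 | 0.828 | 0.741 |
| 8 / 32 | 0.253 | 0.781 | 0.638 |
| 12 / 28 | 0.370 | 0.723 | 0.558 |

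For 8 / 32: 0.781 × 0.747 + 0.253 × 0.219 = 0.583 + 0.055 = 0.638.

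The Background says of the earlier S(+) enantiomer study: "This was shown to reduce postoperative opioid requirements by 20" percent. With that effect (0.20 × 125 = 25 mg) in both sexes, the last column becomes 0.613, 0.558 and 0.516.

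**Step 3: the direct contrast.** In a linear model with treatment, sex and their product, the interaction is the difference between the two within-sex effects. Its SE is 45 × √(2/n_men + 2/n_women), with n per arm. There are 80 − 4 = 76 residual df, so the t quantile is 1.992.

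| Women / men per arm | SE (mg) | 95% half-width (mg) | Power for a 31.25 mg interaction |
|---|---|---|---|
| 4 / 36 | 33.5 | 66.8 | 0.15 |
| 8 / 32 | 25.2 | 50.1 | 0.23 |
| 12 / 28 | 22.0 | 43.7 | 0.29 |

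For 8 / 32: √(2/32 + 2/8) = √0.3125 = 0.559; 45 × 0.559 = 25.2; 1.992 × 25.2 = 50.1 mg.

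**Step 4: scale.** An effect that is equal in percent is unequal in mg if the sexes differ at baseline. For example, a 25% reduction is 31.25 mg from 125 mg but 25 mg from an assumed 100 mg, an interaction of 6.25 mg. The choice of scale therefore has to be stated.

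**The case against.** The sentence is a single exploratory line in a pilot. It promises no test and no claim, and it does not rule out a between-sex contrast. Within-sex estimates can be set side by side descriptively. All of this stands. It is why the point is an improvement rather than an error, and why it would go too far to say that the question cannot be answered under the plan.

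A reader might infer from the table in Step 2 that the plan has a false-positive rate of 56-74% for sex differences. The documents do not support that. Nowhere do they say that a difference will be declared when one sex is significant and the other is not. The figures show what that reading would do if someone adopted it.

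A case with 50% women would lower the bottom of the range to 49%. It is left out because Study Design expects unequal numbers of men and women.

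It can also be said that an interaction estimate from 80 patients tells little: at most 29% power here for a sex difference as large as the whole assumed effect. That is true, but it favours showing the interval. A half-width of 44 to 67 mg makes the lack of information visible, and two p-values hide it.

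**Conclusion.** The point holds as a minor one. The plan poses a between-sex question and names only within-sex comparisons of ketamine with placebo; no section of the combined protocol and SAP supplies the contrast. If a sex difference were read from one significant and one non-significant subgroup, that pattern would arise in about 56-74% of trials with an identical 31.25 mg effect in both sexes (52-61% at 25 mg). These figures rest on the t test, normal doses, a common SD of 45 mg, 40 per arm and an assumed 70-90% men. They illustrate a hazard and do not measure the plan's own error rate. The primary analysis and its conclusion are untouched.

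**What to change.** Keep the existing sentence, since it covers all outcomes, and add after it:

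> For the 48-hour opioid dose, the difference in treatment effect between men and women will be estimated from a linear model with treatment, sex and treatment-by-sex, and reported in mg with its 95% CI as an exploratory result. Subgroup results for other outcomes will be descriptive. No sex difference will be claimed from separate within-sex p-values, and a non-significant interaction will not be read as equal effects.

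An ordinary linear model is enough. The plan assumes the same SD in both arms, and nothing in it calls for robust standard errors.

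The cost is a few lines of text and one secondary model, with no added patients, data or change to the primary test. There are two drawbacks. The estimate will be imprecise (about ±44 mg with 12 women per arm, ±67 mg with 4). On the mg scale, an equal percentage effect with unequal baselines will count as a difference, and the report should say so.
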